2.6.6 APR-246 Cardiac Safety Overview

REDACTED

REDACTED

REDACTED

REDACTED

2.7 Dose Rationale for APR-246 in Combination with Azacitidine

REDACTED

2.7.1 Rationale for Fixed APR-246 Dosing

REDACTED

2.8 Potential Risks and Benefits

2.8.1 Potential Risks

Potential risks identified with APR-246 include transient CNS-related adverse events, bone marrow suppression, QTc prolongation, glucuronidation of acetaminophen.

CNS adverse events:

Non-clinical data have shown APR-246 induced CNS adverse effects at high concentration levels in mice and dogs. The effects were transient and occurred during or in direct connection with dosing (related to high C_{max}). They are fully reversible, usually mild and non-severe, and may be managed by supportive medication (see Section 6.2.2) and/or dose reductions. However, cases with severe intensity have occurred, including events defined as a dose-limiting toxicity. Please consult with the Medical Monitor if you are unfamiliar with these events.

Bone marrow suppression:

No hematological toxicity was detected in nonclinical and clinical studies nor when APR/246 has been dosed alone, but when combined with carboplatin and pegylated liposomal doxorubicin in the study in HGSOc performed under IND 124841, there have been events of agranulocytosis (×1), anemia (×3), febrile neutropenia (×6), leucopenia (×1) and thrombocytopenia (×8). To date there have been no clinical or non-clinical data to support or rule out a contribution from APR-246 to chemotherapy induced bone marrow suppression.

REDACTED

Glucuronidation of Acetaminophen:

Based on co-administration studies in mice, it cannot be excluded that APR-246 may have a negative influence on the glucuronidation of acetaminophen, and therefore potentially potentiating hepatotoxicity after an over-dose of acetaminophen. No hepatotoxicity caused by acetaminophen has been identified in the ongoing clinical studies.

The Investigator's Brochure (IB) may be updated during the course of this study with additional risks and benefits. Please see the current IB for further details about the potential risks and benefits associated with this study.

2.8.2 Potential Benefits

Based on the nonclinical safety profile, the emerging clinical safety profile in over 300 patients, the early evidence of activity in *TP53* mutated MDS patients, as well as the limited life expectancy and lack of effective treatments for these patients, the benefit/risk assessment supports the use of APR-246 for this trial.

2.9 Characteristics of a Well-Conducted Trial

The following characteristics of an adequate and well-conducted trial will be implemented:

1. The Investigators will be well qualified by scientific training and experience.
2. Detailed Case Report Forms (CRFs) will be completed for every patient.
3. Requirements for institutional ethics review as set forth by the appropriate Institutional Review Board/Independent Ethics Committee (IRB/IEC), Title 21 Code of Federal Regulations (CFR) Part 56, the European Union Directive 2001/20/EC and its associated Detailed Guidances, European Union GCP Directive 2005/28/EC, the ICH Guideline for Good Clinical Practice, Sections 3 and 4, and the terms of the Declaration of Helsinki (2013), will be followed.
4. Requirements for informed consent in accordance with institutional guidelines, FDA requirements as specified in Title 21 CFR, Part 50, the European Union Directive 2001/20/EC and its associated Detailed Guidances, European Union GCP Directive 2005/28/EC, the ICH Guideline for Good Clinical Practice, Section 4.8, and the terms of the Declaration of Helsinki (2013), will be followed.
5. Safety data will be recorded and evaluated.
6. Routine monitoring visits will be conducted by the Sponsor's representative (Theradex Oncology) to ensure data accuracy.
7. Drug accountability will be strictly maintained.
8. This trial will be conducted according to Good Clinical Practice (GCP), the protocol and applicable regulatory requirements.

2.10 Patient Population

This study will enroll patients with documented diagnosis of MDS, according to WHO classification, and documented *TP53* mutation that meets IPSS-R classification of intermediate, high, or very high-risk disease, who also meet the eligibility requirements of this protocol.

3.0 TRIAL OBJECTIVES AND PURPOSE

3.1 Primary Objectives

1. To compare the complete response rate, defined as the proportion of patients who achieve CR, and duration of CR with APR-246 + azacitidine treatment vs. azacitidine only.

3.2 Secondary Objectives

To measure the following with APR-246 + azacitidine treatment vs. azacitidine alone:

1. Overall response rate (ORR)
2. DOR
3. Rate and time AML transformation
4. Overall survival (OS)
5. Relapse-free survival (RFS)
6. Transition rate to hematopoietic stem cell transplant (HSCT)
7. Safety profile
8. Rate of red blood cell (RBC) and/or platelet transfusion independence (TI) for 56 days (8 weeks)
9. Pharmacokinetics of APR-246 and azacitidine

3.3 Exploratory Objectives

1. Determine if biomarkers predictive for response to therapy can be derived from baseline molecular analyses of bone marrow or blood samples
2. Determine the depth of remission by IHC, PCR, and other techniques in serial bone marrow or blood samples
3. Investigate potential resistance mechanisms by molecular analysis of bone marrow or blood samples at disease progression

4.0 TRIAL DESIGN

4.1 Overview of Trial Design

This will be a Phase III, multicenter, randomized study to compare the rate of CR and duration of CR, in patients with *TP53*-mutated MDS who will receive APR-246 and azacitidine or azacitidine alone.

Treatment will be administered on an outpatient basis. No investigational or commercial agents or therapies other than those described below may be administered with the intent to treat the patient's disease.

Patients will be randomized (1:1) to one of two arms, stratified by age (< 65 years versus ≥ 65):

1. Experimental arm: APR-246 + azacitidine; or
2. Control arm: Azacitidine

The ITT population will be the primary analysis population for efficacy. All patients who are randomized on study will be considered eligible for the ITT population and will be used for demographics, baseline characteristics summaries.

Patients may continue treatment to the end of the trial as long as toxicity remains acceptable, progression has not occurred and the patient has not withdrawn consent. Response and progressive disease will be assessed based on the Guidelines for Implementation of International Working Group (IWG) response criteria (see [Appendix II](#)) after every two treatment cycles the first year, then every three cycles.

Investigators may choose to transition patients towards a stem cell transplantation (SCT) as appropriate after a response (CR, PR, mCR with HI, mCR without HI, HI) by the experimental or control treatment has been achieved. Patients who undergo SCT will be removed from study treatment and will be followed per the study calendar.

4.2 End of Study

The end of the study is defined as the date of the last visit of the last patient participating in the trial. Long-term follow up will continue until the time of each patient's death.

4.3 Minimizing Bias

All eligible patients entering the clinical trial will be randomized to either the experimental or the control treatment arms at a 1:1 ratio and using the following stratification factors to ensure a balance of patients: by age (< 65 years and ≥ 65 years).

4.4 Drug Products

4.4.1 APR-246

Chemical Name: 2-hydroxymethyl-2-methoxymethyl-1-azabicyclo [2,2,2] octan-3-one)

Storage, preparation and stability: The IMP (investigational medicinal product) should be stored at 2-8°C (35.6-46.4°F). The IMP is formulated as a concentrate for solution for IV infusion, to be diluted with sterile 0.9% NaCl solution prior to administration.

The solution for infusion should be prepared with the prescribed dosage for each patient in accordance with the protocol and separate technical instruction. After preparation of the ready to use solution for infusion the pH of the solution will range from slightly above 4 up to approximately 4.8, depending on dosage. The infusion will be slightly hypertonic, with an osmolarity of maximum 413 mOsm/L. The infusion to the patient should be finalized within 24 h from the time of preparation.

4.4.2 Azacitidine

Chemical Name: 4-amino-1-β-D-ribofuranosyl-s-triazin-2(1H)-one

Formulation, preparation, storage and stability: Please see commercial package insert approved by regulatory agencies ^{30,31}

Route of Administration: Subcutaneous injection preferred*; or intravenous infusion.

Azacitidine is administered SC or IV for 7 consecutive days (Days **4-10**).

* SC preferred but will allow for IV at the Investigator's discretion. However, the same route should be maintained over the 7-day treatment period (whichever route is used on Day **4**, the other days should follow the same route of administration).

4.5 Duration of Therapy

The projected Phase III duration is 30–36 months. Patients may continue treatment to the end of the trial while deriving clinical benefit, unless unacceptable toxicity, progression, death or patient withdrawal requires discontinuation. Patients may remain on protocol therapy after relapse or progression if they are continuing to derive clinical benefit in the opinion of the Investigator.

4.6 Trial Discontinuation

For reasonable cause, the Sponsor may terminate this study prematurely. Written notification of the termination is required. Conditions that may warrant termination include, but are not limited to:

- The discovery of an unexpected, significant, or unacceptable risk to the patients enrolled in the study.
- Failure of the Investigators to enter patients at an acceptable rate.
- Insufficient adherence to protocol requirements (non-compliance).
- Lack of evaluable and/or complete data.
- Decision to modify the developmental plan of the drug.
- A decision on the part of the Sponsor to suspend or discontinue development of the drug.

4.7 Post-Treatment/Long-Term Follow-up

After discontinuation from study treatment, every effort will be made to conduct a post-treatment follow-up visit within 28 days after the last dose of the study drug. All patients should be followed until death. Patients who discontinue any study treatment will be contacted by the study staff for survival status, and/or response assessments, transition to AML, until death as described in Section 7.6.

4.8 Investigational Drug Procurement/Drug Accountability/Disposition of Clinical Trial Supplies

APR-246 should be requested by the Principal Investigator (or his/her authorized designees) at each participating institution. Instructions for ordering APR-246 will be provided in the Pharmacy Binder APR-246 may not be used outside the scope of this protocol, nor can it be transferred or licensed to any party not participating in the clinical study. Investigators may delegate the responsibility for drug ordering, storage, accountability, and preparation to their designees. Drug accountability records will be maintained for all clinical trial supplies. All drug received, dispensed, and returned by the patients must be recorded on a Drug Accountability Record (DAR).

All empty and partially used vials and clinical trial supplies will be destroyed in accordance with the institution's requirements for a cytotoxic agent. The pharmacy will maintain detailed documentation of the number and identification of vials which are destroyed, and copies of these documents will be provided to the Sponsor. Disposition of all unused boxes of study drug will be carried out according to instructions provided by the Sponsor at the end of the study after drug accountability is performed by the Theradex Oncology monitor.

4.9 Registration and Randomization

Prior to registration and any study-specific evaluations being performed, all patients must have given written informed consent for the study and must have completed the pre-study evaluations (see Section 7.2). Patients must meet all of the eligibility requirements listed in Section 7.5. There will be no eligibility waivers granted for this study. Patients will be registered and randomized on the study by using the Theradex Oncology Interactive Web

Response System (IWRS) automated patient registration system (see the Study Operations Binder for specific instructions).

Sites will be asked to provide patient specific inclusion and exclusion criteria documentation for medical review (prior to randomization), including redacted NGS and bone marrow exam reports.

5.0 SELECTION AND WITHDRAWAL OF SUBJECTS

Patients considered for enrollment on this study must have a diagnosis of MDS based on the WHO classification, documented *TP53* mutation, and meets IPSS-R classification of intermediate, high, or very high-risk disease. The patients must meet all inclusion and no exclusion criteria. Investigators must be listed on the FDA 1572 form in order to be authorized to obtain information consent. No study-specific procedures can be performed until the patient has signed an ICF that has been approved by the IRB or IEC. Procedures that are performed prior to patients signing ICFs can be used to satisfy protocol requirements if these procedures are performed as routine medical care for the patient's underlying disease or other illnesses.

The study will enroll patients with *TP53* mutations that are not benign or likely benign, as determined by local Next Generation Sequencing (NGS) and a study-specific variant interpretation algorithm. The *TP53* variant interpretation will be verified centrally prior to inclusion. Central NGS testing including *TP53* will subsequently be conducted on all patients after enrollment. If there is discordance between local and central testing patients will be allowed to remain on study.

5.1 Inclusion Criteria

Patients must fulfill all of the following criteria; there will be no eligibility waivers granted:

1. Patient has signed the Informed Consent (ICF) and is able to comply with protocol requirements.
2. Documented diagnosis of MDS, according to World Health Organization (WHO) classification (< 20% blasts), that meets IPSS-R classification of intermediate, high, or very high-risk disease.
3. Patient has adequate organ function as defined by the following laboratory values:
 - a) Creatinine clearance > 30 mL/min (by Cockcroft-Gault method; see [Appendix IV](#))
 - b) Total serum bilirubin < 1.5 × ULN, unless due to Gilbert's Syndrome, underlying disease of MDS, hemolysis or considered an effect of regular blood transfusions
 - c) Alanine aminotransferase (ALT) and aspartate aminotransferase (AST) < 2.5 × ULN, unless due to underlying disease of MDS
4. Age ≥18 years at the time of signing the informed consent form
5. Having at least one *TP53* mutation which is not benign or likely benign
6. An Eastern Cooperative Oncology Group (ECOG) performance status score of 0, 1, or 2 ([Appendix I](#)).
7. Females of childbearing potential, negative pre-treatment urine or serum pregnancy test.
8. Females of childbearing potential and males with female partners of childbearing potential must be willing to use an effective form of contraception such as latex condom, hormonal birth control, intrauterine device or double barrier method

during chemotherapy treatment and for at least six months thereafter.

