Table 6. Recommendations for APR-246 Dose Modifications and Criteria for Treatment Interruption and Re-Initiation with Treatment-Related Adverse Events

Any changes in dose must be recorded on the Dosage Administration Record CRF.

Renal Toxicities

Parameter	Worst toxicity [†]	Dose Modifications for APR-246
Serum Creatinine	Grade 1 (< 1.5 × baseline)	Maintain dose level
	Grade 2 (> 1.5 to 3.0 × baseline)	Omit dose until resolved to ≤ Grade 1, then: If first occurrence, then maintain dose level If second or more consecutive occurrence, then ↓ 1 dose level
	Grade 3 (> 3.0 – 6.0 × baseline)	Omit dose until resolved to ≤ Grade 1, then: ↓ 1 dose level If not resolved or resolved in > 7 days, evaluate if other contributing factors are present. If none, or after consideration of best interest of the patient, discontinue patient from APR-246. If other factors present, consider continuing after ↓ 1 dose level
	Grade 4 (> 6.0 × baseline)	Permanently discontinue patient from APR-246
† Common Terminology Criteria for Adverse Events (CTCAE) version 5.		

Hepatic Toxicities[◇]

Parameter	Worst toxicity	Dose Modifications for APR-246
Bilirubin [‡]	Grade 1 (> ULN - 1.5 × ULN)	Maintain dose level with LFTs [‡] monitored as per protocol
	Grade 2 (> 1.5 - 3.0 × ULN) with ALT or AST ≤ 3.0 × ULN	Omit dose until resolved to ≤ Grade 1, then: If resolved in ≤ 7 days, if first occurrence, then maintain dose level If second or more consecutive occurrence or if resolved in > 7 days, then ↓ 1 dose level
	Grade 3 (> 3.0 - 10.0 × ULN) with ALT or AST ≤ 3.0 × ULN	Omit dose until resolved to ≤ Grade 1, then: If resolved in ≤ 7 days, ↓ 1 dose level. If no subsequent event, consider re-escalation to original dose level. Omit dose until resolved to ≤ Grade 1, then: ↓ 1 dose level. If second or more consecutive occurrence or if not resolved or resolved in > 7 days, evaluate if other contributing factors are present. If none, or after consideration of best interest of the patient, discontinue patient from APR-246. If other factors present, consider continuing after ↓ 1 dose level.
	Grade 4 (> 10.0 × ULN)	Permanently discontinue patient from APR-246

Parameter	Worst toxicity	Dose Modifications for APR-246
AST or ALT	Grade 1 (> ULN - 3.0 × ULN if baseline was normal; 1.5 - 3.0 × baseline if baseline was abnormal)	Maintain dose level with LFTs [‡] monitored per protocol

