	Grade 2 (> 3.0 - 5.0 × ULN if baseline was normal; >3.0 - 5.0 × baseline if baseline was abnormal) in the absence of total bilirubin elevation to > 2.0 × ULN	Omit dose until resolved to ≤ Grade 1, then If resolved in ≤ 7 days, if first consecutive occurrence, then maintain dose level If second or more consecutive occurrence or if resolved in > 7 days, then ↓ 1 dose level
	Grade 3 (> 5.0 - 20.0 × ULN if baseline was normal; > 5.0 – 20.0 x baseline if baseline was abnormal) in the absence of total bilirubin elevation to > 2.0 × ULN	Omit dose until resolved to ≤ Grade 1, then If resolved in ≤ 7 days, if first consecutive occurrence, then maintain dose level. If second or more consecutive occurrence or if not resolved or resolved in > 7 days, evaluate if other contributing factors are present. If none, or after consideration of best interest of the patient, discontinue patient from APR-246. If other factors present consider continuing after ↓ 1 dose level
	Grade 4 (> 20.0 × ULN if baseline was normal; > 20.0 × baseline if baseline was abnormal)	Permanently discontinue patient from APR-246

◊ Please note that the Investigator is responsible for determining whether a patient meets potential Hy's Law (PHL) criteria at any point during the study. Hy's law identifies patients at risk for severe drug-induced liver injury, DILI, and is defined as AST or ALT ≥ 3× ULN together with Total Bilirubin Level ≥ 2×ULN, where no other reason, other than the suspected drug, can be found to explain the combination of increases, eg, elevated ALP indicating cholestasis, viral hepatitis, or another drug.

† Common Terminology Criteria for Adverse Events (CTCAE) version 5.

‡ For patients with Gilbert's syndrome, these dose modifications apply to changes in direct bilirubin only.

* LFTs include albumin, ALT, AST, total bilirubin (fractionated if total bilirubin > 2.0 × ULN), alkaline phosphatase.

Hematological Toxicities[†]

Parameter	Worst toxicity	Dose Modifications for APR-246
Febrile neutropenia	ANC < 0.5 × 10 ⁹ /L, temperature of ≥ 38 °C or a sustained temperature of ≥ 38°C for more than 1hour	Omit dose until resolved to ≤ Grade 1, then ↓ 1 dose level
Thrombocytopenia	Grade 4 (PLT < 25 × 10 ⁹ /L) [‡] and major bleeding event	Permanently discontinue patient from APR-246

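### Table 6 re-starts APR-246 only at bilirubin of 1.5 × ULN or below, although criterion 3b admits patients above that level, and no row holds the drug when bilirubin and both transaminases are moderately raised together

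*Combined protocol and SAP*

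**What the plan says.** Criterion 3b in section 5.1 (repeated in the synopsis) requires total bilirubin below 1.5 × ULN, "unless due to Gilbert's Syndrome, underlying disease of MDS, hemolysis or considered an effect of regular blood transfusions". No upper limit applies to a patient admitted under one of these causes.

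Table 6 in section 6.2.1 gives recommendations for APR-246 dosing after treatment-related events. Its Hepatic Toxicities block sets bilirubin Grade 1 at above ULN to 1.5 × ULN. Grade 2 is "> 1.5 - 3.0 × ULN) with ALT or AST ≤ 3.0 × ULN", and Grade 3 carries the same transaminase condition. In both grades APR-246 is omitted until bilirubin is back to Grade 1 or less. In the Grade 2 row, a first event that resolves within 7 days keeps the dose. The row then ends: "If second or more consecutive occurrence or if resolved in > 7 days, then ↓ 1 dose level". The Grade 3 row goes further and deals with an event that does not resolve: other contributing factors are sought, and "If other factors present, consider continuing after ↓ 1 dose level". The only bilirubin adaptation is a footnote: "For patients with Gilbert's syndrome, these dose modifications apply to changes in direct bilirubin only".

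The AST/ALT Grade 2 and 3 rows apply only "in the absence of total bilirubin elevation to > 2.0 × ULN". The AST/ALT Grade 1 row has no bilirubin condition and maintains the dose. A footnote makes the investigator responsible for identifying potential Hy's law cases (AST or ALT at least 3 × ULN with total bilirubin at least 2 × ULN). It attaches no hold, stop or re-start rule. Table 6 closes by allowing clinical judgment and consultation with the Medical Monitor.

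**The concern.** Entry and dosing rules should fit together. Criterion 3b accepts raised bilirubin from four causes, and Table 6 follows through for one of them. For the other three, while the cause persists, the printed re-start condition can ask for a bilirubin lower than the patient had at entry. One site may follow the text and hold APR-246, or give it one level lower. Another may use its judgment and re-dose in full. The same patient would then be treated differently by site.

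Bilirubin is also the exception within Table 6. Creatinine Grade 2 is "> 1.5 to 3.0 × baseline". AST/ALT Grade 2 has the branch ">3.0 - 5.0 × baseline if baseline was abnormal". The neutrophil and platelet rows are limited by footnote to patients with normal baseline counts.

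The second issue is one of safety. The bilirubin rows and the AST/ALT rows each exclude part of the other's range, and the overlap left out lies in the numeric Hy's law range. Bilirubin above 2.0 to 3.0 × ULN alone has a written hold. The same bilirubin with both transaminases moderately raised has none.

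**Working it through.** **Part 1: re-start rule.** Let B be the patient's own baseline bilirubin in multiples of ULN. Table 6 requires 1.5 or less. The fall below baseline needed for re-start is 1 − 1.5/B. The documents give no distribution of B, so these values are assumed:

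- B = 1.6: 6%
- B = 1.8: 17%
- B = 2.0: 25%
- B = 2.2: 32%
- B = 2.5: 40%
- B = 3.0: 50%

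Each of these baselines is itself a Grade 2 value in Table 6. If such a patient has a treatment-related rise and returns to B, the Grade 2 row still says to omit. It has no branch for an event that does not resolve. The Grade 3 row has one, but it continues treatment only one level lower.

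Size of a dose level (Table 5): (4.5 − 4.0)/4.5 = 11% and (4.5 − 3.5)/4.5 = 22%. These reproduce the reductions stated in section 6.2.1, which equates them with 19% and 33% lower average Cmax.

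Number of patients: not in the documents. For scale only, assume that 5% to 20% of the 77 experimental-arm patients enter under these exceptions and that 5% to 20% of those have a treatment-related rise of Grade 2 or more. Then 77 × 0.05 × 0.05 = 0.2 and 77 × 0.20 × 0.20 = 3.1, or about 0.2 to 3 patients.

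**Part 2: combined elevation.** Take bilirubin above 2.0 to 3.0 × ULN with both ALT and AST above 3.0 to 5.0 × ULN.

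- Bilirubin Grade 2 row: fails, because neither transaminase is 3.0 × ULN or less.
- AST/ALT Grade 2 row: fails, because bilirubin exceeds 2.0 × ULN.
- Any Other Toxicity row: fails, because it covers Grade 3 or 4 only.

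The rows were coded as logical conditions and tested on a grid: bilirubin 2.1, 2.25, 2.5, 2.75 and 3.0; ALT and AST each 3.1, 3.5, 4.0, 4.5 and 5.0; 5 × 5 × 5 = 125 combinations.

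- Normal baseline ALT/AST: 0 of 125 fit any hepatic row.
- Abnormal baseline ALT/AST (both at the value shown): the number in which at least one transaminase falls in the AST/ALT Grade 1 row is 45 at 1.1 × ULN, 80 at 1.2, 120 at 1.5, 125 at 2.0 and 105 at 2.4. For example, ALT 4.0 with baseline 2.0 is 2.0 × baseline, which is Grade 1, so the dose is maintained whatever the bilirubin.

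So with normal baseline transaminases there is no row, and with abnormal ones there is either no row or one that maintains the dose. In neither case is there a hold.

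How wide is the gap? With normal baseline ALT/AST, use bilirubin bands ≤1.5, >1.5–2.0, >2.0–3.0, >3.0–10 and >10, and transaminase bands ≤3, >3–5, >5–20 and >20 (10 unordered ALT/AST pairs). Of 5 × 10 = 50 combinations, 49 contain a value of Grade 2 or more. If the bilirubin rows' transaminase condition is met when either enzyme is 3.0 × ULN or less, 6 combinations have no hepatic row. Five of these contain a Grade 3 value and reach the general Grade 3–4 rules. One does not, and it is the combination above. If both enzymes must be 3.0 or less, 10 have no row: 8 contain a Grade 3 value and 2 do not. The combination above is uncovered on either reading. These are counts of bands, not of patients.

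**The case against.** The best defence is that Table 6 does not bind. It is titled as recommendations, covers treatment-related events, and closes with clinical judgment. Residual bilirubin from hemolysis or transfusion is not treatment-related, so a physician may call the event resolved at baseline. This stands, and it lowers the weight of the point. It does not supply a re-start rule, and it is the reason sites could differ.

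Section 6.2.1 also bases dose changes on CTCAE version 5, and section 8.1.2.1 grades laboratory values by it. That text is not reproduced, so whether it treats a raised baseline differently cannot be settled here. Table 6 nevertheless prints its own ULN bands. It may be tempting to state that the printed cut-offs override CTCAE for dosing. The documents do not support that step, and it could entrench the ULN-only limits.

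Oversight is real. Liver events may be classed as serious on medical judgment (8.1.2.4), are then reported within one business day (8.1.2.6), and are reviewed by the medical monitor (8.1.2.7) and the IDMC (8.1.3). Section 5.4 stops therapy for toxicity that the investigator judges to preclude it. None of these is a dose rule. For a toxicity not described in Table 6, section 6.2.1 allows resumption at the same dose once it is Grade 1 or less. That is more lenient than the row for bilirubin alone, which reduces the dose after a recurrent or slow event.

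The contrast with neutrophils and platelets is modest, since an abnormal baseline there only leads to the Medical Monitor. The list of risks in section 2.8.1 names no direct liver toxicity of APR-246.

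**Conclusion.** Both parts hold, at minor to moderate severity. Part 1 applies to patients admitted with bilirubin above 1.5 × ULN from MDS, hemolysis or transfusion who then have a treatment-related Grade 2 or 3 rise while the original cause persists. The printed rule asks for 6% to 50% below their own baseline (assumed baselines 1.6 to 3.0 × ULN). What is at stake is a hold, or one dose level, in perhaps 0.2 to 3 patients on assumed shares. Part 2 is a missing hold in the numeric Hy's law range; its frequency is unknown.

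Three stronger readings are not supported:

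- A reader might infer that patients admitted under 3b are held or reduced automatically. A stable elevation is not a treatment-related event and triggers nothing in Table 6.
- A reader might infer that the combined elevation fits no hepatic row in any patient. That is exact only for normal baseline transaminases. Criterion 3c admits ALT and AST up to 2.5 × ULN, and higher if due to MDS, and some of those patients fall in the AST/ALT Grade 1 row.
- A reader might infer that combined elevations in general lack guidance. Bilirubin above 1.5 to 2.0 × ULN is still covered by the AST/ALT rows, and combinations with a Grade 3 or 4 value reach a hepatic row or the general Grade 3–4 rules.

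No effect on sample size, alpha or power is claimed.

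**What to change.** Amend the Hepatic Toxicities block of Table 6; criterion 3b can stay as it is.

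1. For patients whose baseline bilirubin was raised for a cause named in 3b, allow re-start when bilirubin has resolved to Grade 1 or less or to baseline, taking the screening value as baseline. The safety lead may set a ceiling. The Gilbert's footnote stays.
2. Give the Grade 2 bilirubin row the branch that the Grade 3 row already has for an unresolved event with other contributing factors.
3. Add a row for bilirubin of at least 2.0 × ULN with AST or ALT of at least 3.0 × ULN: hold APR-246 while potential Hy's law is assessed, and discontinue if it is confirmed. State that this row takes precedence over the AST/ALT Grade 1 row. The Grade 4 discontinuation rows are unchanged.

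The cost is row and footnote wording. No new test is needed: total bilirubin and transaminases are collected at screening (section 7.2.1) and in the weekly chemistry (schedule footnote k), or at least on Day 1 of each cycle once CR is documented after Cycle 2. The downside is slightly more permissive re-dosing in patients with a raised baseline, and an occasional short hold.
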